**Overall Survival (OS)**

Overall survival (OS) is defined as the time from randomization to the time of death from any cause. Subjects who are alive at the end of the follow-up period, or are lost to follow-up during the study, will be censored at the last date known alive.

Duration of OS is defined as the time from randomization until death (or censoring if no death). It is defined as:

$$OS = \text{Date of Death/Censor} - \text{Date of Randomization} + 1$$

**Objective Response Rate (ORR)**

Objective response rate (ORR) is defined as the proportion of randomized subjects achieving a best overall response of CR or PR per RECIST v1.1. The overall response will be determined by the investigator at each scheduled assessment (every 12 weeks +/- 1 week) based on the achievement of both measurement and confirmation criteria. The evaluation of the overall response is detailed in Table 11 and 12 of the protocol.

A **confirmed** overall response based on the achievement and confirmation of two consecutive assessments is presented below:

Confirmed Overall Response Determination		
Initial Response (Not Yet Confirmed)	Consecutive Response (at Least 4 Weeks Later)	Confirmed Overall Response
PD	-	PD
CR/PR/SD	PD	SD
CR	CR	CR
CR	PR	PR
CR	nfe	SD
PR	CR	PR
PR	PR	PR
PR	nfe	SD
SD	CR/PR/SD/nfe	SD

nfe : no further evaluation

 The NE assessments will not be considered as a consecutive response and will be dropped in the evaluation.

The best overall response is the best **confirmed** overall response recorded from baseline until disease progression.

**Time to Progression (TTP)**

Time to progression (TTP) is defined as the time interval from date of randomization to date of the first documented objective tumor progression. Time to progression does not include deaths as events. Subjects who did not progress are censored at the last radiographic tumor assessment (i.e., with a cycle/visit response of CR, PR, SD, PD). If no post-baseline assessment is available, censoring will occur at date of randomization. The same censoring rules will be applied as for PFS, except that death is not considered as an event.

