6.3.2.2 Special note for baseline determination of Bone lesions and follow-up assessments

In presence of other measurable lesions, the bone lesions are not mandatory to follow. Nevertheless, if followed by imaging, the technique was selected by the site at baseline and will be repeated until documentation of disease progression.

In absence of any other measurable lesions, the bone lesions will be followed every 12 weeks with the most appropriate imaging technique selected by the site at baseline (CT with bone window or MRI or plain X-ray or bone scan) and repeated until documentation of disease progression.

Bone scan/bone imaging is required when progression is suspected in bone.

Bone scan is required at the time of confirmation of CR (if bone metastases were identified at baseline).

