6.3.2.6 Response criteria

In case target lesions are present at baseline, at each assessment the SoD is defined as the sum of diameters of target lesions including short axis of lymph nodes selected as target lesions, and is used to assess the response.

Evaluation of target lesions:

- **Complete Response (CR):** Disappearance of all target lesions. Any pathological lymph nodes (whether target or non-target) must have reduction in short axis to < 10 mm.
- **Partial Response (PR):** At least a 30% decrease in the SoD of target lesions, taking as reference the baseline SoD.
- **Progressive Disease (PD):** At least a 20% increase in the SoD of target lesions, taking as reference the smallest SoD on trial (this includes the baseline SoD if that is the smallest on trial). In addition to the relative increase of 20%, the SoD must also demonstrate an absolute increase of at least 5 mm. (Note: the appearance of one or more new lesions is also considered progression).
- **Stable Disease (SD):** Neither sufficient shrinkage to qualify for PR nor sufficient increase to qualify for PD, taking as reference the smallest SoD while on trial.

Note: Target lesions that become “too small to measure” (TSM) while on trial, all lesions (nodal and non-nodal) recorded at baseline should have their actual measurements recorded at each subsequent evaluation, even when very small (e.g. 2mm). However, sometimes lesions or lymph nodes which are recorded as target lesions at baseline become so faint on CT scan that the radiologist may not feel comfortable assigning an exact measure and may report them as being

“too small to measure”. When this occurs it is important that a value be recorded on the case report form. If it is the opinion of the radiologist that the lesion has likely disappeared, the measurement should be recorded as 0mm. If the lesion is believed to be present and is faintly seen but too small to measure, a default value of 5mm should be assigned.

Evaluation of non-target lesions:

This section provides the definitions of the criteria used to determine the tumor response for the group of non-target lesions.

While some non-target lesions may actually be measurable, they need not be measured and instead should be assessed only qualitatively at the time points specified in the protocol.

- **Complete Response (CR):** Disappearance of all non-target lesions. All lymph nodes must be non-pathological in size (<10mm short axis).

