- **Non-CR/Non-PD:** Persistence of one or more non-target lesion(s).
- **Progressive Disease (PD):** Unequivocal progression of existing non-target lesions. The appearance of one or more new lesions is also considered progression.

Overall response at each time point:

Table 11 below provides a summary of evaluation of the overall response at each time point for patients with target +/- non-target lesions. Table 12 provides a summary of the evaluation of the overall response at each time point for patients with non-target lesions only.

Table 11 : Evaluation of the overall response (OR) in patients with target +/- non-target lesions

Target lesion	Non-target lesion	New lesion	Overall response
CR	CR	No	CR
CR	Non CR / Non PD	No	PR
CR	Not evaluated	No	PR
PR	Non PD or not all evaluated	No	PR
SD	Non PD or not all evaluated	No	SD
Not all evaluated	Non PD	No	NE (Not Evaluable)
PD	Any	Yes or No	PD
Any	PD*	Yes or No	PD
Any	Any	Yes	PD

Table 12 : Evaluation of the overall response (OR) in patients with non-target lesions only

Non-target lesion	New lesion	Overall response
CR	No	CR
Non CR / Non PD	No	Non CR / Non PD
Not evaluated	No	NE
Unequivocal PD*	Yes or No	PD
Any	Yes	PD

*Note: The concept of progression of non-target disease requires additional explanation as follows: when the patient also has both measurable and non measurable disease, to achieve “unequivocal progression” on the basis of the non-target disease, there must be an overall level of substantial worsening in non-target disease such that, even in presence of SD or PR in target disease, the overall tumor burden has increased sufficiently to merit discontinuation of therapy. A modest ‘increase’ in the size of one or more non-target lesions is usually not sufficient to qualify for unequivocal progression status. The designation of overall progression solely on the basis of change in non-target disease in the face of SD or PR of target disease will therefore be extremely rare.

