### **10.5.3 Objective Response Rate (ORR) – Secondary Endpoint**

The objective response rates observed in the treatment groups will be compared adjusting for the stratification variables using the Cochran-Mantel-Haenszel (CMH) test.

A 95% CI will be calculated for each response rate. The best overall response outcome (CR/PR/SD/PD/Unevaluable [UE]) will be summarized and tabulated for the ITT population by treatment group and by the stratification variables using the Cochran-Mantel-Haenszel test as appropriate.

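### Does leaving Non-CR/Non-PD out of the SAP's response lists leave patients with bone-only disease without a usable best response or TTP date?

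*SAP*

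**What the plan says.** Inclusion criterion 7 (Protocol 4.1) accepts measurable disease or bone-only non-measurable disease. Patients in the second group have no target lesions, so their visits are rated by Protocol Table 12, titled "Evaluation of the overall response (OR) in patients with non-target lesions only". Its possible results are CR, Non-CR/Non-PD, NE and PD. Protocol 6.3.2.6 defines Non-CR/Non-PD as "Persistence of one or more non-target lesion(s" and places SD under target lesions: "Neither sufficient shrinkage to qualify for PR nor sufficient increase to qualify for PD, taking as reference the smallest SoD while on trial". These patients are imaged on schedule; Protocol 6.3.2.2 says "In absence of any other measurable lesions, the bone lesions will be followed every 12 weeks".

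The SAP adopts both protocol tables (4.1, ORR): "The evaluation of the overall response is detailed in Table 11 and 12 of the protocol". Three places then leave out Non-CR/Non-PD:

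- The confirmed-response table in SAP 4.1 has rows starting with PD, CR, PR and SD only. Its footnote deals with NE alone: "The NE assessments will not be considered as a consecutive response and will be dropped in the evaluation".
- SAP 10.5.3 lists the best-response categories: "The best overall response outcome (CR/PR/SD/PD/Unevaluable [UE]) will be summarized and tabulated for the ITT population".
- The TTP text in SAP 4.1 reads "Subjects who did not progress are censored at the last radiographic tumor assessment (i.e., with a cycle/visit response of CR, PR, SD, PD". It goes on to apply the PFS censoring rules, except that death is not an event.

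**The concern.** The SAP takes in a visit rating from Table 12 and then gives it no place. A patient with persisting, non-progressing bone lesions would have to be called SD, which the protocol defines from a sum of target-lesion diameters that she does not have, or unevaluable, which is untrue because she was imaged. Two programmers could choose differently and produce different best-response tables from the same data.

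The TTP list looks worse. Of its four ratings, PR and SD cannot arise in a patient without target lesions, and PD cannot arise in one who did not progress, so only CR is left. Her censoring date then seems undefined. Censoring at randomization does not fill the gap, because it applies only when there is no post-baseline assessment. Bone-only disease is also a stratification factor, so the affected patients would gather in one panel of the stratified best-response table.

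**Working it through.** **1. Which sequences lack a row.** With NE dropped as the footnote says, a patient without target lesions can show PD alone, or CR or Non-CR/Non-PD followed by CR, Non-CR/Non-PD, PD or no further evaluation (nfe). That is 1 + 2 × 4 = 9 sequences.

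| Sequence | SAP table returns |
|---|---|
| PD | PD |
| CR, CR | CR |
| CR, PD | SD |
| CR, nfe | SD |
| CR, Non-CR/Non-PD | no row |
| Non-CR/Non-PD, CR | no row |
| Non-CR/Non-PD, Non-CR/Non-PD | no row |
| Non-CR/Non-PD, PD | no row |
| Non-CR/Non-PD, nfe | no row |

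Five of nine have no row. CR followed by Non-CR/Non-PD may not be a valid sequence; without it, four of eight have no row. The two sequences that return SD are not gaps. The table uses SD as its downgrade for any unconfirmed CR or PR, including in target-lesion patients whatever their diameters.

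**2. Does ORR change?** Four rows return a response: CR-CR, CR-PR, PR-CR and PR-PR. Each needs two ratings of CR or PR, so no pair containing Non-CR/Non-PD can be a confirmed response. The ORR numerator is the same under any label. The denominator is all randomized subjects, so it does not move either.

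**3. Does the TTP date change?** Take a patient rated Non-CR/Non-PD at weeks 12, 24 and 36, with no progression or death. Row 3 of the PFS table (no progression, no death, post-baseline assessment present) gives the date of the last tumor assessment, week 36, with no condition on the rating. TTP applies the same rules, so its date is also week 36. The list in brackets also names PD for subjects who did not progress, so it cannot be an exact filter.

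**4. Does the design change?** The SAP's 127 events follow from Schoenfeld's formula with 1:1 allocation, medians of 9 and 14 months, two-sided 10% and 80% power:

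4 × (1.645 + 0.842)² / [ln(9/14)]² = 24.73 / 0.1952 = 126.7, rounded up to 127.

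No response category enters this calculation.

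**5. How many patients might need the label?** The documents do not give the share with bone-only non-measurable disease. Assume 10% to 30%, which is 15 to 45 of the planned 150, and exponential times with the SAP medians. Week 12 is 84/30.44 = 2.76 months. The proportion progression-free at the first visit is then:

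- Arm A: exp(−0.693 × 2.76/9) = 0.809, so 8.1% to 24.3% of the arm.
- Arm B: exp(−0.693 × 2.76/14) = 0.872, so 8.7% to 26.2% of the arm.

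This is an illustration, not a bound. The share is assumed, the medians are for the whole trial rather than for bone-only patients, and enrollment closed early.

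**The case for a change.** The strongest case for a change is that a descriptive report depends on correct categories, and this one is missing. Protocol Table 12 keeps Non-CR/Non-PD apart from SD, and no document maps one to the other. Protocol 2.1.2 still promises a description per arm, Protocol 8 refers to the SAP for descriptive analyses, and the SAP still lists ORR and TTP tables and a per-subject efficacy listing. The best-response list has no fallback of the kind that the PFS rules give TTP. A repair would cost a few lines and no new data.

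The textual point stands: the category is absent and four sequences have no row. The consequence does not follow. Neither document defines a disease-control or clinical-benefit endpoint, so no planned rate depends on whether these patients are counted as SD, unevaluable or Non-CR/Non-PD. SAP 10.5.3 mentions a Cochran-Mantel-Haenszel test on best response where appropriate, and a label could affect that test, but the protocol now rules out statistical comparison and calls the primary and secondary objectives not applicable. Calling an imaged patient unevaluable would be a plain error, which leaves two sensible choices: show the Table 12 term as its own line, or group it with SD under a footnote.

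A rewrite also carries risks. Relabelling CR followed by no further evaluation as Non-CR/Non-PD would contradict the protocol's own definition, because that patient's only rating is disappearance of all lesions. Rewording the TTP censoring sentence without the PFS sentence could separate two endpoints that are meant to share one rule.

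**Conclusion.** No change is needed. This is missing detail that an analyst fills sensibly, with no gain from amending the plan. The gap is four unlisted sequences in the confirmed-response table and one absent best-response label, for patients with non-target lesions only. ORR, PFS censoring, TTP dates, sample size, event count and power are all unaffected. The TTP list is loose wording that the imported PFS rules override.

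This rests on two readings. The first is that the SAP's statement applying the PFS rules to TTP governs over the list in brackets. The second is that the analysis stays descriptive, as Protocol 2.1.2 and 8 say. The number of patients involved is unknown; the 8% to 26% per arm shown above depends on an assumed share and would change only how they are labelled.

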## **4.2 Safety Endpoints**

### **Adverse Events (AE)**

Adverse events are coded using the Medical Dictionary for Regulatory Activities (MedDRA) terminology. AEs will be assessed according to the Common Terminology Criteria for Adverse Events (CTCAE) version 4.0. The CTCAE represents a comprehensive grading system for reporting the acute and late effects of cancer treatments. CTCAE v4.0 grading is by definition a 5-point scale generally corresponding to mild, moderate, severe, life threatening and death.

### **Treatment Emergent Adverse Event (TEAE)**

An AE will be considered treatment emergent if:

Its onset date occurred any time on or after the administration of the first dose of any study treatment up to 30 days after the last dose of study treatment (or up to any time if serious AE related to study treatment).

### **Related Adverse Events**

Adverse events can be considered “related” and the relationship will be assessed for each component of the study treatment. If an AE is missing the relationship information (from the investigator) then this adverse event will be treated as “related” in the statistical analysis.

### **Serious Adverse Events (SAE)**

A serious adverse event (SAE) is defined as any AE which:

- Results in death
- Is immediately life-threatening
- Results in persistent or significant disability / incapacity
- Requires or prolongs subject hospitalization
- Is a congenital anomaly / birth defect

- Is to be deemed serious for any other reason if it is an important medical event when based upon appropriate medical judgment which may jeopardize the subject and may require medical or surgical intervention to prevent one of the other outcomes listed in the above definitions.

### **Laboratory Data**

Hematology and blood chemistry labs will be collected in the eCRF. All those labs will be converted using recommended units by through Oracle Clinical Remote Data Capture (OCRDC).

In addition, laboratory data will be classified (by biostatistics/SAS programming) into grades according to the Common Terminology Criteria for Adverse Events (CTCAE) v4.0.

### **Vital Signs**

Vital sign assessments are performed in order to characterize basic body function. The parameters expected to be collected include: weight (kg) and systolic / diastolic blood pressure (mmHg).

Systolic blood pressure will be categorized as <140 mmHg, 140-160 mmHg, >160 mmHg, and Diastolic blood pressure as <90 mmHg, 90-100 mmHg, >100 mmHg.

### **Concomitant Medication**

A medication will be regarded as previous if it started within 30 days before the randomization and stopped before randomization (medication stop date < randomization date).

A medication will be regarded as concomitant if:

- It started on or after the date of randomization and within 30 days after the date of last study treatment; **OR**
- It started prior to randomization but was ongoing at the time of the randomization.

### **Left Ventricular Ejection Fraction (LVEF)**

Left Ventricular Ejection Fraction (LVEF) will be collected in the eCRF to assess the percent volume of blood that is pumped by the left ventricle with each cardiac contraction to detect any cardiac toxicity associated to the drugs. LVEF will be performed by MUGA scan or echocardiogram, using the same method at each assessment.

### **ECOG Performance Status**

Performance status will be collected in the eCRF according to ECOG scale to assess how the disease affects the daily living abilities of the subject.

### **Drug Exposure**

Exposure analyses will be based on the actual dose administered (in mg). The planned dose for Letrozole and Afatinib is the same for each subject regardless of their physical characteristics (weight).

The following variables summarizing the overall administration (not by cycle) will be derived:

#### Letrozole

- Number of cycles: number of cycle having a duration of intake > 0 day
- Duration of treatment (in weeks) = [(Date of last dose - date of first dose +1)]/7
- Duration of exposure (days) = Sum of each sub-administration duration (Stop Date – Start Date +1)
- Relative dose intensity (%) = [ Duration of exposure (days) / Duration of treatment (days) ] x 100

#### Afatinib

- Number of cycles: number of cycle having a duration of intake > 0 day
- Duration of treatment (in weeks) = [(Date of last dose - date of first dose +1)] /7

- Duration of exposure (days) = Sum of each sub-administration duration (Stop Date – Start Date +1)
- Cumulative dose (mg) = Sum of all (each sub-administration Duration of exposure (days) × 30 mg or 20 mg if dose reduced)
- Relative dose intensity (%) = [ Cumulative Dose (mg) / (Duration of treatment (days) × 30 mg ) × 100

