Afatinib tablets are shipped and stored between 8 to 25°C or as specified by label for the given climate zone.

Temperature loggers shall be used.

Alert setting of the temperature loggers are

Climatic Zone I/II countries -20°C / +30°C (e.g. Europe, USA, Argentina, China)

Climatic Zone III/IV countries -20°C / +25°C (e.g. Brazil, India, most Asian and African countries)

Specific expiry date is provided on the label of each bottle.

Medication should be kept in their original container in a secured area at the trial site in accordance with applicable regulatory requirements.

Returned medication (empty containers and partially used containers) should be stored separately from medication that needs to be dispensed.

To ensure adequate records, dispensations, return and accountability of afatinib tablets are documented in a timely manner.

The following information are documented:

- Patient’s number
- Date dispensed

- Number of tabs dispensed/returned for each strength
- Batch number and expiry date

Bottles/boxes are labeled according to local regulations and include the following as a minimum:

- Trial number
- Product name (BIBW 2992)
- Contents of the bottle (30 tablets)
- Tablet strength
- Batch number
- Medication number
- Use-by date
- Storage information
- Instructions for use
- Manufacturer name and address
- A statement that the medication is for clinical trial use only
- A caution statement

A new bottle of medication is dispensed on day 1 of each course, regardless of the number of tablets remaining in the bottle from the previous course. The patient initially receives one bottle of 30mg tablets and in the event that dose reduction is necessary the patient returns to the clinic and new medication is dispensed.

According to the information reported in section 3-Trial Design (IN ADDITION) regarding the decision to discontinue the patients from the trial at the latest on 30 November 2018, the information reported in this section is applicable until 30 November 2018. After that date, the patients will not receive afatinib anymore in the scope of the trial but in the frame of an alternative drug supply outside the clinical trial as appropriate according to local legislation. At the end of the clinical trial all drug supplies unallocated or unused by the patients must be disposed of and accounted for according to local governing auspices and site SOPs. The documentation should be available.

5.2.2.2 **Letrozole**

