5.3.2 Standard treatment schedule

Afatinib:

At each monthly visit, patients should be given a 30-tablet bottle.

For administrative purposes treatment is divided into treatment cycles, which are each 4 weeks (28 days) in duration. However, treatment is given continuously unless treatment schedule adjustments are needed (as per section 5.4). Patients take a single oral dose of afatinib each day for the first and subsequent cycles. The medication should be taken at the same time each day (\pm 2 hours) at least one hour before food intake and at least three hours after the last food intake.

Afatinib tablets should be swallowed whole with water. If dosing of whole tablets is not possible, afatinib tablets can be dispersed in approximately 100 ml of noncarbonated drinking water. No other liquids should be used. The tablet should be dropped into the water without crushing it, and stirred occasionally for up to 15 min until the tablet is broken up into very small particles. The dispersion should be consumed immediately. The glass should be rinsed with approximately 100 ml of water which should also be consumed. The dispersion can also be administered through a gastric tube. . Administration of afatinib via gastric tube has to be recorded in the CRF.

No tablet should be ingested if it is broken, cracked, or otherwise not intact.

Missed/Vomited/Extra Doses:

If an entire daily dose is skipped, the patient should resume treatment the following day with her regular dose. No “make-up dose” or increased dosing should occur.

If a dose is vomited at any time, the patient should resume treatment the following day with her regular dose. No “make-up dose” or increased dosing should occur.

Patients should report all vomited, missed or delayed doses to the trial staff and will be provided with a medication diary which should be turned in at every visit.

If a patient inadvertently takes 1 extra dose during a day, she should not take the next day's dose.

Letrozole: Patients should be instructed to swallow letrozole tablet without regard to food. Patients should be encouraged to take their dose at approximately the same time each day.

For patients in Arm B (letrozole + afatinib), it is recommended to take letrozole and afatinib at the same time to ensure compliance.

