8.3 Protocol Treatment

Duration of treatment exposure, cumulative dose and dose intensity will be summarized by treatment group using the Safety population. The patients with dose modifications will be presented by treatment group, along with reasons for the dose change.

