### **10.4 Study Drugs Administration**

Number of cycles, Duration of treatment, Cumulative dose (for Afatinib only) and Relative dose intensity (RDI) will be summarized by treatment for the safety population.

The relative dose intensity will be additionally presented categorized (i.e., number and percentage of subjects with relative dose intensity of <60%, 60-<80%, 80-<90%, 90-<110%, ≥110%).

The number and percentage of subjects with dose interruptions/discontinuations or reduced (Afatinib only), along with their respective reasons will be summarized.

For Afatinib, the compliance will be summarized by visit following this calculation :

$$\text{Compliance (\%)} = \left[ \frac{\text{Number of tabs taken}}{\text{Sum of each sub-administration duration in a visit}} \right] \times 100$$

When the total number of tabs taken does not equal the number of tabs dispensed minus the number of tabs returned, the reasons will also be summarized.

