**BIostatistics**  
**Statistical Analysis Plan**  
**TRIO-020**  
**STAT-020-SAP**

Title	Population	Description
		Status at Registration, Prior Surgery for Breast cancer and Prior Anti-Tumor Therapy.
Study Drug Exposure	Safety	Tabulates the Number of Cycles, the Duration of Treatment, the Cumulative dose, the Relative dose intensity, Reductions.  The number of subjects with dose interruptions/discontinuation or reduction will also be summarized.
Progression-Free Survival	ITT	Summary of PFS results including treatment comparison results.
Progression-Free Survival	ITT	Summary of PFS results including treatment comparison results (sensitivity analysis).
Overall Survival	ITT	Summary of OS results including treatment comparison results.
Objective Response Rate	ITT	Summary of ORR results including treatment comparison results.
Time to Progression	ITT	Summary of TTP results including treatment comparison results.
TEAEs Overview	Safety	Tabulates the number of TEAEs, serious TEAEs, Grade 3-4 TEAEs, Treatment Related TEAEs, Serious and Treatment Related TEAEs, Fatal TEAEs.
Treatment Emergent Adverse Events (TEAEs)	Safety	Summary by system organ class and preferred term for each treatment group.

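### Afatinib cumulative dose and relative dose intensity are built from interval days, so tablets missed inside a recorded interval still count as taken

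*SAP*

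**What the plan says.** SAP 4.2 (Drug Exposure) opens with a principle: "Exposure analyses will be based on the actual dose administered (in mg"). For afatinib it takes the duration of each sub-administration as stop date minus start date plus one, then sets "Cumulative dose (mg) = Sum of all (each sub-administration Duration of exposure (days) × 30 mg or 20 mg if dose reduced"). RDI is that total divided by treatment days × 30 mg, where treatment runs from first to last dose.

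SAP 10.4 adds a separate measure: "For Afatinib, the compliance will be summarized by visit following this calculation". The ratio is tablets taken over the summed sub-administration days in the visit. The same section reports RDI in bands: "number and percentage of subjects with relative dose intensity of <60%, 60-<80%, 80-<90%, 90-<110%, ≥110"%.

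The planned Study Drug Exposure table (SAP 11.1) has this content: "Tabulates the Number of Cycles, the Duration of Treatment, the Cumulative dose, the Relative dose intensity, Reductions". Numbers of patients with interruptions, discontinuations or reductions are added. Neither this table nor any other in 11.1 names compliance.

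The protocol foresees missed days. Section 5.3.2 states: "If an entire daily dose is skipped, the patient should resume treatment the following day with her regular dose". Missed doses are to be reported and a diary kept. Accountability under 5.2.2.1 covers this item: "Number of tabs dispensed/returned for each strength". After the amendment to a descriptive trial, section 8.3 still requires these outputs: "Duration of treatment exposure, cumulative dose and dose intensity will be summarized by treatment group using the Safety population".

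**The concern.** The stated principle and the formula do not match. A patient who skips tablets without a break being entered keeps the full cumulative dose and the full RDI for that interval. The SAP expects tablets and interval days to differ, since its compliance measure is the ratio of the two, yet that difference never reaches cumulative dose or RDI.

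The error runs essentially one way: Arm B would look better dosed than it was, and some patients would sit in too high an RDI band. Protocol 1.3.2 describes afatinib's gastrointestinal and skin events as dose-dependent, so these figures will be read next to the safety tables.

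**Working it through.** **Inputs.** Dose levels of 30 mg and 20 mg (Protocol 5.4.1, Table 1); 28-day cycles (Protocol 5.3.2); formulas from SAP 4.2; compliance ratio and RDI bands from SAP 10.4. The documents state no exposure result to reproduce and no adherence rate, so all missed-tablet counts below are assumptions.

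**General size.** At a constant strength:

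- SAP dose = interval days × strength.
- Tablet-based dose = tablets taken × strength = SAP dose × adherence, where adherence is tablets taken / interval days (the compliance ratio of SAP 10.4).
- Overstatement = 1/adherence − 1.

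| Adherence within intervals | Overstatement |
|---|---|
| 95% | 1/0.95 − 1 = 5.3% |
| 90% | 1/0.90 − 1 = 11.1% |
| 85% | 1/0.85 − 1 = 17.6% |
| 80% | 1/0.80 − 1 = 25.0% |

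**One 28-day cycle recorded as a single 30 mg interval.** The SAP formula gives 28 × 30 = 840 mg and RDI 100% whatever is missed.

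| Tablets missed | Tablet-based dose | Tablet-based RDI | Band |
|---|---|---|---|
| 1 | 810 mg | 96.4% | 90 to <110% |
| 3 | 750 mg | 89.3% | 80 to <90% |
| 6 | 660 mg | 78.6% | 60 to <80% |
| 12 | 480 mg | 57.1% | <60% |

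**84 days, no recorded hold.** The denominator is 84 × 30 = 2520 mg and the SAP RDI is 100%. With 76 tablets taken, 76/84 = 90.5% and the band is unchanged. With 75, 75/84 = 89.3% and the patient drops one band.

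**84 days with a recorded 5-day hold, resumed at 30 mg** (a pattern Protocol 5.4.7 allows for unrelated events). SAP: 79 × 30 = 2370 mg; 2370/2520 = 94.0%. If 75 of the 79 tablets were taken (75/79 = 94.9%): 75 × 30 = 2250 mg; 2250/2520 = 89.3%. The band changes at about 95% adherence.

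**168 days with a reduction** (56 days at 30 mg, 10-day hold, 102 days at 20 mg; 6 and 10 tablets missed). The denominator is 168 × 30 = 5040 mg.

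- SAP: 56 × 30 + 102 × 20 = 3720 mg; RDI 73.8%.
- Tablet-based: 50 × 30 + 92 × 20 = 3340 mg; RDI 66.3%.

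Both figures reflect the hold and the reduction. Only the second reflects the missed tablets. The band happens not to change.

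**Alternative reading: every missed day splits the interval.** With 4 days missed in 28, the exposure days are 24, the dose is 24 × 30 = 720 mg and RDI is 720/840 = 85.7%, which is exact. Compliance is then 24/24 = 100%, so a fully recorded miss leaves no trace in it.

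**Upper limit.** With non-overlapping intervals and no dose above 30 mg, the largest possible RDI over 84 days is (84 × 30)/(84 × 30) = 100%. The band of 110% or more cannot be filled.

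**The case against.** The strongest reply is that the answer turns on an eCRF rule the documents do not show. The SAP does not define a sub-administration. Diaries are handed in at every visit, and SAP section 6 defines first and last dose by a nonzero dose on the administration record, which hints that zero-dose entries may exist. If every missed day is entered as a break, the formula is exact. Compliance could still serve as a cross-check, because tablet counts and recorded dates need not agree. The phrase about actual dose can also be read as the dose level in force over the recorded intervals, rather than a tablet count.

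This makes the error conditional but does not remove it. Wherever compliance differs from 100%, the SAP dose differs from tablets times strength by that factor. Where every missed day is a break, the tablet-based formula gives the same answer, so adopting it does not alter the result.

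Other points on that side stand in part:

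- Missed tablets are summarised as compliance by visit, and SAP 11.2 plans a per-patient administration listing. Neither corrects overall cumulative dose or RDI, and no table in 11.1 names compliance.
- Tablet counts have faults of their own. They do not remove vomited doses, and SAP 10.4 already expects some not to reconcile.
- The unreachable top band is cosmetic.
- The size is hypothetical, and the 84-day examples lie close to a cut-point.

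**Conclusion.** The concern holds as a minor one. As written, the afatinib formulas do not deliver the tablet-level exposure that the opening principle of SAP 4.2 suggests. Cumulative dose and RDI are overstated by 1/adherence − 1 wherever tablets are missed without a recorded break: about 5% at 95% adherence and 11% at 90%. A change of RDI band needs 75 or fewer tablets in 84 days without a hold, or about 95% adherence after a 5-day hold.

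This rests on two things the documents leave open: actual adherence, and whether single missed days split an interval. Recorded holds and reductions are handled correctly. Only descriptive exposure outputs are affected; no test or treatment-effect estimate changes.

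**What to change.** - In SAP 4.2, define afatinib cumulative dose as the sum over visits of tablets taken × tablet strength, and RDI as that sum / (treatment days × 30 mg) × 100.
- Keep the interval-based figure as a flagged fallback where counts are missing or do not reconcile with dispensed minus returned.
- Define sub-administration and state whether a single missed day opens a new interval.
- Add overall compliance per patient to the Study Drug Exposure table.
- Label letrozole RDI as interval-based. Protocol 5.2.2.2 only recommends collecting returned letrozole, so a tablet count may not be available.
- Drop the band of 110% or more for any RDI that stays interval-based.

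The cost is one derivation change and one table row. Tablets taken are already needed for SAP 10.4, and dispensed and returned counts are documented by strength. Check first that tablets taken can be split by strength in the database.

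The drawbacks are that RDI may come out slightly lower, vomited doses still count as taken, some patients will need the fallback, and the two drugs will have different RDI definitions.
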